### **5. ASSESSMENT OF SAFETY**

#### **5.1 SAFETY PLAN**

The safety plan for patients in this study is derived from clinical experience with atezolizumab in completed and ongoing studies. The anticipated important safety risks are outlined below (see Section 5.1.1).

Measures will be taken to ensure the safety of patients participating in this study, including the use of carefully chosen inclusion and exclusion criteria and close monitoring of patients during the study. Administration of atezolizumab will be performed in a monitored setting in which there is immediate access to trained personnel and adequate equipment and medicine to manage potentially serious reactions.

After initiation of study treatment, all adverse events will be reported until 30 days after the last dose of study treatment or until initiation of new anti-cancer therapy, whichever occurs first. SAEs and adverse events of special interest will continue to be reported until 90 days after the last dose of study treatment or until initiation of new anti-cancer therapy, whichever occurs first.

Guidelines for managing anticipated adverse events, including criteria for dosage modification and treatment interruption or discontinuation, are provided below (Section 5.1.2), in [Appendix 11](#), and in Section 6 of latest version of the Atezolizumab Investigator's Brochure. Refer to Protocol Sections [5.2–5.6](#) for details on safety reporting during the study.

In the setting of a pandemic or epidemic, screening for active infections (including SARS-CoV-2) prior to and during study participation should be considered according to local or institutional guidelines or guidelines of applicable professional societies (e.g., American Society of Clinical Oncology or European Society for Medical Oncology).

Severe *SARS-CoV-2 infection* appears to be associated with a CRS involving the inflammatory cytokines IL-6, IL-10, IL-2, and IFN- $\gamma$  (Merad and Martin 2020). If a patient develops suspected CRS during the study, a differential diagnosis should include *SARS-CoV-2 infection*, which should be confirmed or refuted through assessment of exposure history, appropriate laboratory testing, and clinical or radiologic evaluations per investigator judgment. If a diagnosis of *SARS-CoV-2 infection* is confirmed, the disease should be managed as per local or institutional guidelines.

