#### **5.3.1 Adverse Event Reporting Period**

Investigators will seek information on adverse events at each patient contact. All adverse events, whether reported by the patient or noted by study personnel, will be recorded in the patient's medical record and on the Adverse Event eCRF.

**After informed consent** has been obtained **but prior to initiation of study drug**, only serious adverse events caused by a protocol-mandated intervention (e.g., invasive procedures such as biopsies, discontinuation of medications) should be reported (see [Section 5.4.2](#) for instructions for reporting serious adverse events).

**After initiation of study drug**, all adverse events will be reported until 30 days after the last dose of study drug and 90 days for serious adverse events or adverse events of special interest.

Instructions for reporting adverse events that occur after the adverse event reporting period are provided in [Section 5.6](#).

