##### **5.4.2.2 Events That Occur after Study Drug Initiation**

After initiation of study drug, serious adverse events and adverse events of special interest will be reported until 90 days after the *final dose of study drug or until initiation of new systemic anti-cancer therapy, whichever occurs first*. Investigators should record all case details that can be gathered immediately (i.e., within 24 hours after learning of the event) on the Adverse Event eCRF and submit the report via the electronic data capture (EDC) system. A report will be generated and sent to Roche Safety Risk Management by the electronic data capture (EDC) system.

In the event that the EDC system is unavailable, the Serious Adverse Event/Adverse Event of Special Interest Reporting Form provided to investigators should be completed and submitted to the Sponsor or its designee immediately (i.e., no more than 24 hours after learning of the event), either by faxing or by scanning and emailing the form using the fax number or email address provided to investigators. Once the EDC system is available, all information will need to be entered and submitted via the EDC system.

Instructions for reporting serious adverse events that occur > 90 days after the last dose of study treatment are provided in Section [5.6](#).

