## **6.4 PRIMARY SAFETY ANALYSIS**

The primary endpoint of the study is the incidence of treatment-emergent AEs. Verbatim descriptions of AEs will be mapped to MedDRA thesaurus terms and graded according to the National Cancer Institute Common Terminology Criteria version 4.0. Multiple occurrences of the same event will be counted once at the maximum severity.

Other safety variables will include:

- Drug exposure (e.g., treatment duration, number of doses, dose intensity and dose modifications/discontinuations, with reasons)
- All AEs
- SAEs
- AEs (grade 3–5)
- AEs of special interest
- AEs leading to study drug discontinuation or interruption
- Changes in vital signs from baseline
- Changes in physical findings from baseline
- Changes in selected laboratory parameters from baseline
- Deaths and cause of death
- Concomitant medications

The incidence of AEs will be summarized by frequency tables. Corresponding 95% Clopper-Pearson confidence intervals (CIs) will be presented, as applicable. Time to first incidence of selected event types will also be estimated and presented graphically using the Kaplan-Meier method.

Treatment exposure, discontinuation rate, and cause of death will be analyzed by frequency tables. When appropriate, median time on treatment and 95% CI will be estimated by the Kaplan-Meier approach or using univariate statistics, presenting mean, median, quartiles, minimum, maximum and standard deviation.

Changes in vital signs and physical findings from baseline will be tabulated and presented graphically when applicable.

Worst grades for laboratory parameters and newly occurring Grade 3 and 4 laboratory values during treatment will be summarized by frequency tables.

Concomitant medications recorded during the study will be summarized by frequency tables.

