## **Appendix 1** **Schedule of Assessments (cont.)**

- p. After informed consent has been obtained, but prior to initiation of study drug, only SAEs caused by a protocol-mandated intervention should be reported. After initiation of study drug, all SAEs and AEs of special interest, regardless of relationship to study drug, will be reported until 90 days after the last dose of study drug or initiation of new anti-cancer therapy, whichever occurs first. All other AEs, regardless of relationship to study drug, will be reported until 30 days after the last dose of study drug or initiation of new anti-cancer therapy, whichever occurs first. After this period, the investigator should report any SAEs or AEs of special interest believed to be related to prior study drug treatment. The investigator should follow each AE until the event has resolved to baseline grade or better, the event is assessed as stable by the investigator, the patient is lost to follow-up, or the patient withdraws consent. Every effort should be made to follow all SAEs considered to be related to study drug or study-related procedures until a final outcome can be reported.
- q. Survival and new anti-cancer therapy follow-up information will be collected via telephone contact, patient medical records, and/or clinic visits approximately every 3 months until death, loss to follow-up, end of study, patient withdrawal or study termination by the Sponsor, whichever occurs first.

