4.6.2 Adverse Events

Verbatim descriptions of AEs will be mapped to latest version of MedDRA thesaurus terms and graded according to the National Cancer Institute Common Terminology Criteria version 4.0 (NCI CTCAE v4.0).

Multiple occurrences of the same event will be counted once at the maximum severity.

The following AEs will be initially considered as AEs of special interest:

- Pneumonitis
- Colitis
- Endocrinopathies: diabetes mellitus, pancreatitis, adrenal Insufficiency, hypothyroidism/hyperthyroidism and hypophysitis
- Hepatitis
- Transaminitis Grade ≥ 2 (Aspartate aminotransferase (AST) or alanine aminotransferase (ALT) $>3x$ ULN and bilirubin $>2x$ ULN) OR AST/ALT $>10x$ ULN
- Systemic lupus erythematosus
- Neurological: Guillain-Barre Syndrome, myasthenic syndrome or myasthenia gravis, meningoencephalitis
- Nephritis
- Ocular toxicities (e.g., uveitis, retinitis, optic neuritis)
- Myositis
- Myopathies, including rhabdomyolysis
- Vasculitis
- Events suggestive of hypersensitivity, [infusion-related reactions](#), cytokine release, HLH and MAS
- Cases of potential drug-induced liver injury that include an elevated ALT or AST in combination with either an elevated bilirubin or clinical jaundice, as defined by Hy's law (see Section 5.3.5.7 of the protocol)
- Suspected transmission of an infectious agent by the study drug, as defined below:
Any organism, virus, or infectious particle (e.g., prion protein transmitting transmissible spongiform encephalopathy), pathogenic or non-pathogenic, is considered an infectious agent. A transmission of an infectious agent may be suspected from clinical symptoms or laboratory findings that indicate an infection in a patient exposed to a medicinal product. This term applies only when a contamination of the study drug is suspected.
- Cardiac toxicities of Grade ≥ 2 (e.g., atrial fibrillation, myocarditis, pericarditis)
- Autoimmune flare of Grade ≥ 3

Beside the listed AEs of special interest, Roche will provide a list of MedDRA Preferred Terms (basket) during the study to identify the AEs of special interest for the statistical analysis.

Treatment-emergent AEs (TEAEs) will be defined as any AEs with an onset date after the start date and time of first administration of study treatment and up to 30 days after

the date of last administration of study treatment (For SAEs and AEs of special interest up to 90 days).

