AEs with onset on first dosing date, not recorded as starting before study treatment administration will be considered as TEAEs. Similarly, AEs with onset date prior first dosing date but worsening/change recorded on or after first dosing date will be considered as TEAEs.

Only TEAEs will be included in summary tables. AEs which are not treatment-emergent will only be included in the AE listings.

Patient rates for AEs will be presented and accompanied by the respective two-sided 95% Pearson-Clopper CIs.

In any AE summary tables, number and percentage of patients reporting at least one AE will be provided. In AE summary tables by SOC and PT, the number of reported events will be presented additionally.

Every occurrence of an AE in any patient will be counted in the total number of events.

In tables presenting frequency of AEs by worst grade, only the event with the highest grade will be counted when there are multiple occurrences of a same AE in one patient.

A missing NCI CTCAE grade will be imputed as follows: for a fatal AE, as Grade 5; for a non-fatal AE, as Grade 4.

A summary table will be provided presenting:

- Number and percentage of patients with any TEAE
- Number and percentage of patients with any Serious TEAE
- Number and percentage of patients with any related TEAE
- Number and percentage of patients with any related Serious TEAE
- Number and percentage of patients with any TEAE leading to study drug discontinuation
- Number and percentage of patients with any grade 3 to 4 TEAE
- Number and percentage of patients with any grade 5 TEAE
- Number and percentage of patients with any AESI
- Number and percentage of patients with any grade 3 to 5 AESI
- Number and percentage of deaths, overall and by reason
- Number and percentage of deaths on study treatment (i.e. within 30 days post last study treatment administration), overall and by reason

Following safety data will be summarized:

- TEAEs by SOC, PT and by worst grade
- TEAEs of grade 3 to 5, by PT and by worst grade
- TEAEs of grade 5, by PT
- TEAEs leading to study drug discontinuation, by SOC and PT
- TEAEs leading to study discontinuation, by SOC and PT
- TEAEs related to study drug, by SOC, PT and worst grade
- Serious TEAEs by SOC, PT and worst grade
- Serious TEAEs related to study drug, by SOC and PT
- AEs of special interest by category, PT and worst grade (with additional column for AESI of grade ≥ 3)

Death cases will be summarized as follows:

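### The SAP's treatment-emergent window has no stop at new anti-cancer therapy although most of the reporting rules do, so events after a switch can enter the all-cause serious, Grade 5 and rare-term tables unevenly across sites

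*SAP*

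**What the plan says.** Protocol 6.4 sets the endpoint: "The primary endpoint of the study is the incidence of treatment-emergent AEs". SAP 4.6.2 closes the window for it by time since last dose alone, at 30 days after "the date of last administration of study treatment (For SAEs and AEs of special interest up to 90 days". It adds "Only TEAEs will be included in summary tables", so the window decides what is tabulated.

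The rules on collection are these:

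- **Protocol 5.1.** All AEs are collected "until 30 days after the last dose of study treatment or until initiation of new anti-cancer therapy, whichever occurs first". SAEs and AEs of special interest (AESIs) are "reported until 90 days after the last dose of study treatment or until initiation of new anti-cancer therapy, whichever occurs first".
- **Protocol 5.3.1**, the section that carries the reporting period in its title: "all adverse events will be reported until 30 days after the last dose of study drug and 90 days for serious adverse events", with AESIs named alongside the SAEs. It has no stop at new therapy.
- **Protocol 5.4.2.2.** SAEs and AESIs are reported until 90 days after the "final dose of study drug or until initiation of new systemic anti-cancer therapy, whichever occurs first". Section 5.6 defines the same period and also says systemic.
- **Protocol Appendix 1, note p.** SAEs and AESIs run to 90 days or new therapy. Other AEs "will be reported until 30 days after the last dose of study drug or initiation of new anti-cancer therapy, whichever occurs first". SAP Appendix 2 reproduces this note, so the SAP contains both versions.
- **After the stop.** Section 5.6 still asks for SAEs believed related to earlier study drug. Note p asks for such SAEs and AESIs.

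**The concern.** The analysis window is longer than the collection window that most sections prescribe. Where a site stopped collecting at the switch, the extra days hold almost no data. Where a site went by 5.3.1, they hold events that arose on the next treatment. The SAP pools the two as if collection had been the same everywhere. Protocol 9.5 plans about 200 sites in about 30 countries, so a uniform reading cannot be assumed.

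At stake are the all-cause tables in which a few patients matter: serious TEAEs, Grade 5 TEAEs and uncommon preferred terms. Those are rates of the order that Protocol Table 6 was drawn up for. With a single arm, no comparator would carry the same distortion and cancel it.

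**Working it through.** **1. Follow one event through the rules.** Take an SAE unrelated to atezolizumab, 60 days after last dose, in a patient who has already started next-line treatment.

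| Section the site follows | On the AE eCRF? | TEAE under SAP 4.6.2? |
|---|---|---|
| 5.3.1 read alone | Yes (60 < 90) | Yes |
| 5.1, or Appendix 1 note p | No | Nothing to count |
| 5.4.2.2 or 5.6 | No if the new treatment is systemic; yes if it is, for example, radiotherapy only | Follows the record |

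A death not due solely to progression behaves the same way. Under 5.3.1 with 5.3.5.8 it goes on the AE eCRF and becomes a Grade 5 TEAE. Under 5.6 it goes on the Long-Term Survival Follow-Up eCRF and does not. An SAE believed related to atezolizumab is collected under either reading, which is why the related-event tables are little exposed.

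**2. Reproduce the plan's precision figure.** Protocol Table 6 gives exact two-sided 95% limits for x events in n = 1000. The lower limit is the 0.025 quantile of Beta(x, n − x + 1). The upper limit is the 0.975 quantile of Beta(x + 1, n − x). For x = 5 these are 0.1625% and 1.1629%, printed as 0.16 and 1.16. The half-width is (1.1629 − 0.1625)/2 = 0.500 points, the stated ±0.5%. All nine rows reproduce.

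**3. Add post-switch patients to the 5/1000 row.**

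| Extra patients | Rate | 95% CI |
|---|---|---|
| 0 | 0.5% | 0.16 to 1.16 |
| 2 | 0.7% | 0.28 to 1.44 |
| 5 | 1.0% | 0.48 to 1.83 |
| 7 | 1.2% | 0.62 to 2.09 |

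Five extra patients move the estimate by 5/1000 = 0.5 points, the whole stated precision.

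**4. How many extra patients?** The documents do not say how many patients switch inside the window, so every share below is an assumption.

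- *Upper illustration.* Protocol 1.1 quotes febrile neutropenia in 6% on vinflunine, and Protocol 1.3.4 reports no cases on atezolizumab in IMvigor 210. Share switching × 6% gives 0.05 × 6% = 0.3%, 0.10 × 6% = 0.6% and 0.20 × 6% = 1.2%. This assumes that every switcher carries that risk, that all of it falls inside the window, and that every event is reported.
- *Same sum, a quarter of patients at sites using 5.3.1 alone.* 3 × 0.25 = 0.75, 6 × 0.25 = 1.5 and 12 × 0.25 = 3 patients per 1000.
- *General form.* Extra patients = 1000 × q × r × s, where q is the share switching in the window (10–30%), r is the risk of the given event there (1–5%) and s is the share of patients at sites using 5.3.1 (25–100%). The lowest value is 1000 × 0.10 × 0.01 × 0.25 = 0.25. The highest is 1000 × 0.30 × 0.05 × 1 = 15.
- *Any SAE, r = 10–20%.* From 1000 × 0.10 × 0.10 × 0.25 = 2.5 to 1000 × 0.30 × 0.20 × 1 = 60, before removing patients who already had an SAE.

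**5. The any-TEAE rate.** IMvigor 210 had 300/310 = 96.8% with any AE. From that level the rate can rise by at most 100 − 96.8 = 3.2 points.

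**The case against.** The strongest reply is that the route is narrow. Protocol 5.3 tells investigators to report under that section together with 5.4 to 5.6. Section 5.3.1 itself sends the reader to 5.6 for later events, and 5.6 states the stop. Only SAEs and AESIs have the 90-day window, and both 5.4.2.2 and 5.6 stop them at systemic therapy. The Version 15 rationale names 5.4.2.2 and 5.6 as the places where this timeline was corrected, which suggests that the stop is intended and that 5.3.1 was passed over. Unrelated post-switch events come in only where a site relied on 5.3.1. This stands as a limit on how often it happens. It does not remove the contradiction.

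A reader might infer that such events are attributed to atezolizumab. The documents do not support that. A TEAE is defined by timing, Protocol Table 5 has events with another cause marked as unrelated, and SAP 4.6.2 tabulates related TEAEs separately. The problem is confined to all-cause counts.

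A reader might also take 1.2% as an estimate. It is a ceiling. The switching shares are assumed, 6% comes from one drug's trial, and febrile neutropenia is not on the AESI list, so after day 30 it counts only if serious.

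Finally, a time-only window can be defended as conservative in a safety study, and a plain cut would drop late events that 5.6 and note p deliberately keep collecting. The second part stands and shapes the fix. The first holds only if collection was uniform, which these rules do not secure.

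**Conclusion.** The contradiction is in the text: SAP 4.6.2 and Protocol 5.3.1 run 30/90 days without a stop, and five other places stop at new therapy, worded two ways. All-cause serious, Grade 5 and rare-term counts can therefore depend on which section a site followed.

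The size cannot be derived. For a single event the assumed scenarios run from 0.25 to 15 extra patients per 1000, and 5 would match the stated precision. The any-TEAE rate can barely move, if it is near the 96.8% of IMvigor 210, and the related-event tables little. Overall mortality is not at issue, because SAP 4.6.2 also counts all deaths by days since last dose.

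The documents do not show that any site collected unrelated events after a switch. It would go too far to say that next-line toxicity has distorted the headline incidence. The supported conclusion is that the plan leaves this open and should close it.

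**What to change.** **SAP 4.6.2**

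- End the main TEAE window at the earlier of 30 days (90 for SAEs and AESIs) after last dose or the start of new systemic anti-cancer therapy. State how an event starting on that same day is handled.
- Keep in the main count any SAE or AESI inside the 30/90-day window that is judged related to atezolizumab, even after the switch.
- Show the other post-switch events in a separate row.
- Report the present time-only count as a sensitivity analysis.

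**Protocol**

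Reconcile 5.1, 5.3.1, 5.4.2.2, 5.6 and Appendix 1 to one wording, including new versus new systemic therapy. SAP Appendix 2 follows.

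**Cost**

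The SAP part is a short edit and a date comparison. The start of subsequent therapy is already used for PFS and best response (SAP 4.4.2.2 and 4.4.2.3), and such therapy is already summarised and listed (4.6.5). The result is a slightly lower all-cause incidence and one extra table. The protocol part needs an amendment and would do little for data already in hand: the SAP was signed in May 2023 and describes the iDMC reviews as past. The SAP change does help those data, because events before the switch and inside the window are reportable under every section. The cut therefore makes the main count largely independent of the section a site followed. A small gap remains for patients whose first new treatment was not systemic.
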